APOE $\epsilon 4$ status will be determined and will be blinded to the Sponsor, investigator, and participant and will not be shared with the investigator or the participant until the study is unblinded (unless required for participant safety or by the relevant health authority or IRB/EC). Participants will have access to this information if they elect to at the end of the study. If already known, the *APOE* $\epsilon 4$ status will still need to be confirmed and should be kept blinded from the Sponsor. In addition, as much as possible, participant *APOE* $\epsilon 4$ status should remain blinded to the site and central MRI readers.

Samples and data may be used for future research or diagnostic test development.

RNA Sampling

During screening and at a subsequent visit as detailed in the schedule of activities (see [Appendix 1](#)), two 2.5-mL whole blood samples will be obtained for RNA extraction from every participant who has consented to participate in the study. The sample may be used to evaluate clusterin messenger RNA and other exploratory genetic markers in peripheral blood (see Section [4.5.12](#)).

Plasma Sampling

At screening and at subsequent visits as detailed in the schedule of activities (see [Appendix 1](#)), two 6-mL whole blood sample will be obtained for plasma extraction from every participant who has consented to participate in the study.

This sample will be used to evaluate exploratory plasma biomarkers in peripheral blood, which may include, but will not be limited to *A* β , tau, *p-Tau*, and neurofilament.

An additional plasma sample for the assessment of exploratory plasma biomarkers will be obtained as soon as is practical (e.g., at an unscheduled visit) once the site becomes

aware of the occurrence or worsening of ARIA-E or of the occurrence of ARIA-H meeting discontinuation criteria.

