4.5.9 Brain Magnetic Resonance Imaging

MRI should be performed using 1.5-T or 3.0-T scanners, and wherever possible the same scanner should be used for an individual participant for the full duration of the study. MRI will be conducted at participant screening for safety monitoring, as a baseline measure of structural brain volumes, and as baseline information for the PET substudies (for the schedule of activities, see [Appendix 1](#)).

Where available, exploratory MRI techniques including rs-fMRI and DTI will also be acquired. In addition, the screening MRI will be used to help determine whether the exclusion criteria are met (e.g., number of microbleeds, presence of mass lesions).

MRI will be used during the study to help assess safety such as the occurrence of microbleeds or signs potentially indicative of inflammation or ARIA-E. Additional unscheduled MRI scans may be performed to better understand relevant CNS adverse events (such as increased confusion) occurring in the context of ARIA or to follow a sign that emerges at a scheduled scan; contrast agent may be used in such a case of follow-up MRI scans if administration of contrast agent is considered safe for the participant according to local standards. In addition, structural MRI (to assess whole brain and regional brain atrophy), fMRI, and DTI-MRI will be performed at multiple timepoints to determine potential treatment effects on MRI outcome measures (according to the schedule of activities).

MRI scans will include the following sequences:

- 3D T₁-weighted gradient recalled echo (GRE) scans
- T₂*-weighted GRE scans
- T₂-weighted FLAIR scans
- BOLD rs-fMRI, if available (to assess resting-state functional connectivity at investigative sites having the required software and sequences)
- DTI-MRI, if available (to assess fiber tract integrity)

For details on the specific imaging sequences and acquisition times required, refer to the MRI Manual.

MRI should not be performed unless at least 3 days have passed since a lumbar puncture. If an MRI and lumbar puncture are both scheduled for the same day, the MRI should be performed first.

All images (except BOLD fMRI and DTI-MRI) will be used to assess MRI inclusion and exclusion criteria.

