4.6.2 Assessments at Baseline

In order to be randomized and to receive double-blind treatment, participants must have no significant change in medical, psychiatric, or neurological conditions or change in medication since screening. The recommended order of assessments and rating scales is as follows:

- Clinical assessments (e.g., CDR, MMSE, and ADAS-Cog), including all those that require study partner input, should be completed before any invasive safety assessments.
- Vital sign measurements, ECGs, blood draws for clinical laboratory assessments, PK, ADA, and plasma biomarker sampling, and urine samples are recommended to be conducted following scale assessments and must *all* be performed prior to study drug administration.

The recommended order of clinical assessments/rating scales at baseline is as follows:

Participant Assessments	Study Partner Assessments
1. ADAS-Cog13	1. CDR (study partner input)
2. CDR (participant interview)	2. FAQ
10-min break (optional)	3. ADCS-ADL
3. MMSE	4. ZCI-AD
4. Coding	5. QoL-AD
5. Verbal Fluency Task	6. EQ-5D
10-min break (optional)	7. RUD-Lite
6. QoL-AD	8. NPI-Q

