Appendix 1: Schedule of Activities (cont.)

Table 1: Week –12 to Week 32; Dose Escalation with Q4W Administration (cont.)

- ⁱ Serum chemistry includes AST, ALT, alkaline phosphatase, total protein, total bilirubin, serum albumin, creatine phosphokinase, sodium, potassium, calcium, BUN, and serum creatinine (and creatinine clearance calculated by the central laboratory). During the screening period (Week –1 to Week –12), hemoglobin A_{1c}, glucose, insulin, total cholesterol, HDL, LDL, triglycerides, C-reactive protein, folic acid, vitamin B-12, T4, free T4, and thyroid-stimulating hormone levels will also be assessed and should ideally be collected at least 4 hours after meals.
- ^j Hematology includes hemoglobin, hematocrit, RBC count (with morphology), WBC counts, platelets, basophils, eosinophils, lymphocytes, monocytes, neutrophils, and WBC—other total counts.
- ^k A complete physical examination includes an evaluation of the head, eyes, ears, nose, and throat, and the cardiovascular, dermatological, musculoskeletal, respiratory, gastrointestinal, genitourinary, and neurological systems.
- ^l Limited, symptom-directed physical examinations; changes from baseline abnormalities should be recorded in participant notes.
- ^m CSF and matching serum sampling, and PET and MRI scans at screening should be performed once all other screening results are available and none exclude the participant from the study.
- ⁿ MRI must be performed at least 7 days before dosing and results must be available for review by site staff before dosing can proceed. It is not recommended that the MRI be performed on the same day as the IMP administration (especially during uptitration period during which it is recommended to do the MRI at least 10 days after the third dose of sing step). MRI should be performed before or at least 3 days following a lumbar puncture.
- ^o Includes resting-state functional MRI and DTI outcome measures where available.
- ^p Lumbar puncture must be performed in the morning (between 8:00 a.m. and noon) to minimize potential diurnal variation of CSF parameters. For post-baseline visits, lumbar puncture as well as serum sampling should be performed prior to dosing. Only one method (CSF or PET) confirming amyloid is necessary for all participants.

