## **5. STATISTICAL ANALYSES**

### **5.1 GENERAL CONSIDERATIONS**

The clinical cutoff date for the primary analysis is defined by the date of the last randomized participant plus 116 weeks.

In the following sections, for all continuous variables for which descriptive statistics are indicated, the following statistics will be reported: the number of observations, the mean, median, standard deviation, and minimum and maximum. The 25th and 75th percentiles

(Q1 and Q3) will also be reported for selected tables. Descriptive summaries of discrete data will include frequencies expressed in terms of number and percentage of participants.

For clinical endpoints and biomarkers assessments, the baseline is defined as the assessment taken at the baseline visit (Day 1) up to and including the day of first study drug intake. If no assessment is reported at the baseline visit up to the day of first study drug intake, the earliest assessment reported after Day 1 and up to the day of second dose or Day 35, whichever is earlier, will be used as baseline. If no assessment is reported either at baseline visit or up to Day 35, an assessment reported at screening will be used as baseline. Day 35 is the latest timepoint allowed for Week 4 visit as per protocol.

For all other assessments, the baseline is defined as the last available assessment prior to first study drug intake, unless specified otherwise.

For biomarkers (CFS and plasma), values below the lower limit of quantification (LLOQ) will be set to  $0.5 \times \text{LLOQ}$ , while values above the upper limit of quantification (ULOQ) will be set to ULOQ. A summary table will be provided to summarize the values below LLOQ and above ULOQ for each treatment arm.

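### SAP 5.1 lets an early post-dose MRI or plasma value displace the planned pre-dose screening value as baseline: a small, avoidable flaw confined to the biomarkers

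*SAP*

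**What the plan says.** SAP 5.1 sets one order of choice for clinical endpoints and biomarkers together.

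- First choice: "For clinical endpoints and biomarkers assessments, the baseline is defined as the assessment taken at the baseline visit (Day 1"), which runs to the day of first dosing.
- Second choice, if there is no such value: "the earliest assessment reported after Day 1 and up to the day of second dose or Day 35, whichever is earlier, will be used".
- Last choice: "If no assessment is reported either at baseline visit or up to Day 35, an assessment reported at screening will be used as baseline".

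Everything else follows the conventional rule: "For all other assessments, the baseline is defined as the last available assessment prior to first study drug intake".

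The protocol places the pre-dose biomarker assessments at screening. Section 4.5.9 states: "MRI will be conducted at participant screening for safety monitoring, as a baseline measure of structural brain volumes". A footnote to Appendix 1 Table 1 says: "CSF and matching serum sampling, and PET and MRI scans at screening should be performed once all other screening results are available". On plasma the protocol is not consistent. Section 4.5.6.2 has samples taken "At screening and at subsequent visits as detailed in the schedule of activities", and Table 1 marks screening and Week 24 but not Day 1. Section 4.6.2, on the baseline visit, says that "PK, ADA, and plasma biomarker sampling, and urine samples are recommended to be conducted following scale assessments" and that all of these must precede dosing.

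The baseline rows of SAP Tables 7, 9, 10, 11 and 12 (amyloid PET, tau PET, CSF, plasma, volumetric MRI) run up to Day 35 with no pre-dose condition. For amyloid PET, SAP 5.7.5.3 adds that the scan nearest the target day is taken when several fall in a window.

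**The concern.** The order is sensible for a scale with a planned Day 1 administration: the second and third choices matter only when Day 1 was missed. For a measure whose planned pre-dose value is at screening, the first choice is normally empty. Any qualifying post-dose value then outranks the planned one.

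A baseline taken after randomisation and dosing can be affected by treatment or by the event that prompted it. Protocol 4.5.9 allows unscheduled MRI to investigate CNS adverse events in the context of ARIA. Protocol 4.5.6.2 requires an extra plasma sample when ARIA-E appears or worsens, or when ARIA-H meets the discontinuation criteria. ARIA is an identified risk of the drug, so such values could arise unequally between arms.

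The substituted value enters the percent change in volumetric MRI (SAP 5.7.9). For plasma it enters both the change and the baseline covariate (SAP 5.7.8).

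**Working it through.** No sample size, power or alpha figure depends on this rule, so the check is a trace of the rule against the schedule, followed by day arithmetic.

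**1. What is scheduled (Protocol Appendix 1, Table 1)**

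| Measure | Planned pre-dose value | Marked at Day 1 | Next time in Table 1 | Unscheduled column |
|---|---|---|---|---|
| CDR, ADAS-Cog13, ADCS-ADL, FAQ | Day 1 | yes | Week 24 | yes |
| MRI | screening | no | Week 12 | yes |
| Plasma biomarkers | screening | no (but see 4.6.2) | Week 24 | yes |
| CSF or PET | screening | no | none | no |

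The first choice in SAP 5.1 is therefore normally empty for MRI. It is also empty for plasma if Table 1 governs. The second choice can be filled only by an unscheduled assessment. Table 1 shows that route for MRI and plasma, but not for PET or CSF.

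**2. How long the second choice is open**

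The SAP's convention is target day = 7 × week + 1. Week 24 gives 7 × 24 + 1 = 169, as in SAP Table 4. Week 4 gives 7 × 4 + 1 = 29, and the ±7-day dosing window runs from Day 22 to Day 36. The SAP's Day 35 corresponds to 28 + 7, a one-day counting difference that does not bear on the point. Eligible post-dose days are:

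- at most: Day 2 to 35, 35 − 1 = 34 days;
- second dose on schedule: Day 2 to 29, 29 − 1 = 28 days;
- earliest in-window second dose: Day 2 to 22, 22 − 1 = 21 days.

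**3. A gap between the second and third choices**

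The second choice stops at the second dose if that comes first. The third opens only if nothing was reported up to Day 35. Take a participant with a second dose on Day 22, a valid screening scan and an unscheduled scan on Day 30. The Day 30 scan is too late for the second choice, yet its existence blocks the third. Read literally, there is no baseline. SAP 5.1 does not impute a missing baseline outcome, so this participant would drop out of the change-from-baseline model.

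**4. Size of an early drug effect**

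The documents give no model for early effects on volumetric MRI or plasma. For amyloid PET, Protocol Appendix 4 allows an illustration. The fractional fall in SUVR is 0.019 × Ce^0.716, where Ce is the effect-site concentration (µg/mL) from the Appendix 4 PK parameters and Ke0 = 0.00174 per day. For a typical subject after one dose:

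| Dose | Day | Ce | Fall in SUVR |
|---|---|---|---|
| 120 mg | 29 | 0.169 | 0.53% |
| 120 mg | 35 | 0.189 | 0.58% |
| 120 × 1.18 = 141.6 mg | 29 | 0.200 | 0.60% |
| 141.6 mg | 35 | 0.222 | 0.65% |

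The second dose level applies the G4/G3 exposure ratio of 1.18 from Protocol 1.3.2. The shift is small even where the rule would permit it.

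**The case against.** The strongest case on the other side has five parts.

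- **The first choice might already cover screening.** It extends to the day of first dosing, which could be read as taking in anything earlier. That fails, because screening is named separately as the last resort. Protocol 4.5.9 cannot rescue it either: the SAP's introduction says its language supersedes the protocol's.
- **The routes are narrow.** No MRI is scheduled between screening and Week 12. The documents do not say that an unscheduled safety scan is processed for volumetry, and SAP Table 2 requires a valid quantitative measurement. In Study WN25203 new ARIA-E was most frequent between 3 and 6 months (Protocol 1.2.3). This stands, and it limits the expected frequency.
- **Plasma may have a Day 1 sample.** Protocol 4.6.2 suggests so. If it was collected, the first choice is filled and the problem disappears for plasma. This stands until 4.6.2 and Table 1 are reconciled.
- **PET and CSF cannot be verified.** Table 1 marks neither in the unscheduled column, although the general wording of Protocol 4.6.8 is broader. The PET substudy protocols were not supplied. An eligibility scan may have used florbetapir, which the amyloid analysis does not accept, so a usable screening scan cannot be assumed. A reader might infer that PET or CSF baselines will be contaminated; the documents show only that the rule permits it.
- **Proximity to Day 1 has value.** Screening may be up to 12 weeks earlier. At rescreening a lumbar puncture up to 12 months old may be reused, and an outside PET scan may be accepted. This is a real cost. But for MRI, and for plasma under Table 1, screening is already the planned baseline for nearly everyone, so using it throughout is the consistent choice.

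One could add that CDR and MMSE also have screening values and follow the same order. That is true, but they have a planned Day 1 value, so the order matters there only when that value is missing.

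**Conclusion.** The point holds for volumetric MRI, on the condition that an unscheduled scan between first and second dose yields a volumetric measurement. It holds for plasma if Table 1 governs. For PET and CSF it is a permission in the rule without a documented route. The gap in step 3 is a separate wording defect in the same sentences.

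Three stronger readings are tempting and not supported:

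- That any value up to Day 35 becomes baseline. Only the earliest value qualifies, only up to the second dose if that is sooner, and only when there is no Day 1 value.
- That a definite share of the 1016 participants is affected. The documents give no count of early unscheduled assessments, so any percentage would be a guess. The number is probably very small.
- That the efficacy conclusion is at risk. CDR-SB, ADAS-Cog 13, ADCS-ADL and FAQ all have planned Day 1 values, so the primary endpoint and the testing hierarchy are essentially unaffected.

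The case for changing the rule is that a valid pre-dose value should not give way to a post-randomisation one when avoiding it costs almost nothing. It does not rest on a large expected bias.

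**What to change.** - In SAP 5.1, for volumetric MRI, plasma, CSF and PET, define baseline as the last valid assessment before first study drug intake, screening included.
- Allow a post-dose value, up to the earlier of the second dose and Day 35, only when no valid pre-dose value exists, and flag it in the analysis dataset. This also closes the gap in step 3 for these measures.
- Align the baseline rows of SAP Tables 7 and 9 to 12, and make the nearest-to-target rule in 5.7.5.3 subject to it.
- Reconcile Protocol 4.6.2 with Appendix 1 Table 1 on whether a plasma biomarker sample is taken at the baseline visit.
- The order for the clinical scales can stay.

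The cost is a sentence or two in SAP 5.1, the table edits and one change to the baseline derivation, all of which can be specified before unblinding. The small downside is the age of some screening values: up to about 12 weeks, or longer for a reused lumbar puncture or PET scan.

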## **5.2 PARTICIPANT DISPOSITION**

The analysis of participant disposition will be based on all enrolled participants (see Analysis sets in [Table 2](#)). The number of participants enrolled will be tabulated by country, site, and treatment arm. Participant disposition (the number of participants randomized and completing the different study periods) will be tabulated by treatment arm. Premature study drug discontinuation and study discontinuation, as well as reasons for discontinuations, will be summarized.

Major protocol deviations, including major deviations with regard to the inclusion and exclusion criteria, will be summarized by treatment arm. Separate tables will be provided for COVID-19-related major protocol deviations and reasons for COVID-19-related major protocol deviations.

## **5.3 ENDPOINT ANALYSIS**

### **5.3.1 Definition of Primary Endpoint**

As detailed in the study protocols, the primary endpoint is the change from baseline to Week 116 in the CDR-SB which is a global scale covering both functional and cognitive domains.

The CDR-SB is a detailed quantitative general index that is scored from 0 to 18 with higher scores indicating greater impairment. The CDR characterizes six domains: memory, orientation, judgment and problem solving, community affairs, home and hobbies, and personal care. The necessary information to make each rating is obtained through a semi-structured interview with the patient and a reliable informant or collateral source (e.g., a study partner).

### 5.3.2 Definition of Primary Estimand

The clinical question of interest is to assess the effect of the active drug on disease progression at Week 116, irrespective of use or initiation of symptomatic treatments for AD, in the absence of a substantial impact of the COVID-19 pandemic.

In alignment with the Addendum to [ICH E9](#), the primary efficacy estimand is described by the following attributes:

- **Target Population:**  
Early (prodromal to mild) AD population as identified by the inclusion and exclusion criteria, see Sections 4.1.1 and 4.1.2 of the study protocols
- **Variable:**  
Change from baseline to Week 116 in Clinical Dementia Rating – Sum of Boxes (CDR-SB)
- **Treatment:**  
Prescribed study drug including uptitration to the target dose and safety-related dose modifications, irrespective of use or initiation of symptomatic treatment for AD
- **Population-level summary:**  
Difference in variable means between treatment arms

#### **Intercurrent events (ICE):**

The ICEs are classified into two categories: those that are Study Drug or Condition Related (SDCR) and those that are not (NSDCR). The list of main anticipated ICEs, and their classification as SDCR or NSDCR, is presented below ([Table 3](#)). The final list of ICEs may need to be adapted in case unanticipated ICEs emerge during the study conduct. The classification of each ICE into SDCR or NSDCR will be completed and documented prior to the unblinding.

The ICE of substantial reduction in drug exposure due to the COVID-19 pandemic is defined as 4 or more dose-months (i.e., 16 weeks, not necessarily consecutive) of treatment missed due to COVID-19-related reasons. This definition will be equally applied to placebo and active arms. One dose-month is defined as 4 weeks of dosing, i.e., one dose with a Q4W dosing frequency (mostly during uptitration) or two doses with a Q2W dosing frequency (at target dose). The threshold of four missed dose-months was determined based on the following reasons:

- A 12-week extension to the study was implemented (in protocol amendment version 4) to mitigate the impact of the COVID-19 pandemic. Therefore, treatment interruptions up to 3 dose-months (i.e., 12 weeks) are already accounted for in the study design.
- Based on the half-life of approximately 24 days of gantenerumab, plasma concentration after a 4 months' interruption at the target dose is expected to be below the observed concentration with the dose of 225 mg Q4W which was

shown to be ineffective in Studies WN25203 (SCarlet RoAD) and WN28745 (Marguerite RoAD).

- A 20% difference is the usual acceptability threshold to establish PK bioequivalence. The protocol includes 20 dose-months (80 weeks) at target dose after the up-titration period. Missing less than 4 dose-months results in an overall reduction in drug exposure of less than 20% of the total planned dose.

As a conservative approach, all withdrawals from study treatment due to an AE will be classified as SDCR for the purpose of the primary analysis. This includes withdrawal from study treatment due to suspected or confirmed COVID-19 infection AE, because the relationship of these events to the participant condition may be ambiguous.

All SDCR ICEs will be handled with a treatment policy strategy, while NSDCR ICEs will be handled with a hypothetical strategy. The frequencies of ICE will be summarized by treatment arm.

In this study, given the disease stage at baseline of the target population, death is expected to be a rare event and mostly not considered related to treatment or disease progression, and as such the corresponding ICE of death will be handled with a hypothetical strategy for the primary estimand. Of note, a supplementary estimand which defines all ICEs, including death, as SDCR (and thus using the same imputation strategy as for the other SDCR ICEs; see Section 5.3.3), is described in Section 5.3.5.

